6.4.2 Description of Safety and Tolerability Variables

Safety and tolerability variables include the following:

- Adverse events (including adverse events of special interest [AESI])
- Physical examination findings including an ophthalmological examination (ie, clinically significant changes from Baseline)
- Vital signs (ie, clinically significant changes from SAOL Baseline for data collected during the SAOL phase and RW Baseline for data collected during the RW phase)
- Laboratory assessments including clinically significant changes from SAOL Baseline for data collected during the SAOL phase and RW Baseline for data collected during the RW phase in hematology with platelet counts, CRP, ESR, ferritin, fibrinogen, D-dimer, liver enzymes, creatinine, and glomerular filtration rate

- Immunogenicity evaluation: Generation of anti-rh-IL-18BP antibodies
- Local tolerability at the injection site, as evaluated by a standardized assessment

An AESI for this study is defined as an event that constitutes an injection site reaction, including pruritus, erythema, and swelling.

6.4.3 Description of Pharmacokinetic Variables

The following pharmacokinetic (PK) parameters will be estimated at Week 0 (V1) and Week 4 (V5) by non-compartmental methods using actual elapsed time from dosing:

- AUC_{0-24} : Area under the concentration-time curve ($\text{ng} \times \text{h}/\text{mL}$) from time zero (pre-dose) to 24 hours post-treatment, calculated by the linear trapezoidal rule
- C_{\max} : Maximum concentration ($\text{ng} \times \text{mL}$), obtained directly from the observed concentration versus time data
- T_{\max} : Time to maximum concentration (hours), obtained directly from the observed concentration versus time data
- $T_{1/2}$: Apparent terminal half-life (hours), determined as $\ln(2)/\lambda_z$
- λ_z : Apparent terminal elimination rate constant (1/hours), determined by linear regression of terminal points of the log-linear concentration-time curve. A minimum of 3 data points are required for determination of λ_z , with an r-square value ≥ 0.8 . In addition, visual assessment by the pharmacokineticist may be used to confirm the terminal linear phase of the concentration-time profile

For calculations using the linear trapezoidal rule, the following formula will be used:

$$AUC_{0-24} = \frac{1}{2}(A_1 + A_2)(t_2 - t_1)$$

6.5 Data Quality Assurance

Report summaries will be generated using validated Base SAS® software, version 9.4 or higher, on a PC or server-based platform. PK parameters and analyses will also be generated using SAS® software. Additional validated software may be used to generate analyses, as needed.

All SAS programs that create outputs or supporting analysis datasets will be validated by a second statistical programmer or biostatistician. At a minimum, validation of programs will consist of a review of the program log, review of output or dataset format and structure, and independent confirmatory programming to verify output results or dataset content. Additionally, all outputs will undergo a review by a senior level team member before finalization.

The content of the source data will be reviewed on an ongoing basis by project statistical programmers and statisticians. Data will be checked for missing values, invalid records, and extreme outliers through defensive programming applications, analysis-based edit checks, and other programmatic testing procedures. All findings will be forwarded to the project data manager for appropriate action and resolution.

7 STATISTICAL METHODS

7.1 General Methodology

Data will be analyzed by Precision for Medicine biostatistics personnel. Statistical analyses will be reported with tables, figures, and listings, presented in rich text format, and using recommended ICH numbering. Output specifications for all tables, figures, and listings will be in conformance with guidelines specified by the ICH in Appendix 7 of the *Electronic Common Technical Document Specification* (Apr 2003).

7.1.1 *Reporting Conventions*

Tables and figures will be summarized for all patients combined during the SAOL phase and by treatment group during the RW phase. Tables summarizing demographics and other baseline characteristics for the RW phase will also include a column for all patients combined. Where applicable, separate summaries will be presented for each study phase (SAOL and RW). In general, all data collected and any derived data will be presented in patient data listings, for all enrolled patients. Listings will be ordered by site, patient number, treatment group, and assessment or event date. The treatment group presented in listings will be based on the planned assignment, unless otherwise noted.

In general, continuous variables will be summarized to indicate the study population sample size (N), number of patients with available data (n), mean, SD, median, 25th (Q1) and 75th (Q3) quartiles, minimum, and maximum values. Selected continuous efficacy variables will also be summarized by the 95% CI of the mean. Categorical variables will be summarized by the population size (N), number of patients with available data (n), number of patients in each category, and the percentage of patients in each category. Unless otherwise noted, the denominator to determine the percentage of patients in each category will be based on the number of patients with available data. Selected ordinal data may be summarized using both descriptive statistics and counts and percentages of patients in each category, as appropriate.

Non-zero percentages will be rounded to one decimal place. Rounding conventions for presentation of summary statistics will be based on the precision of the variable of summarization, as it is collected in its rawest form (ie, on the eCRF or as provided within an external file) and are outlined as follows:

- The mean and median will be rounded to one more decimal place than the precision of the variable of summarization

- Measures of variability (eg, SD, SE) will be rounded to two more decimal places than the precision of the variable of summarization
- Minimum and maximum values will be presented using the same precision as the variable of summarization

Other statistics (eg, CIs) will be presented using the same general rules outlined above or assessed for the most appropriate presentation based on the underlying data.

Statistical significance testing will be two-sided and performed using $\alpha=0.05$. P-values will be reported for all statistical tests, rounded to four decimal places. P-values less than 0.0001 will be displayed as “<0.0001”; p-values greater than 0.9999 will be displayed as “>0.9999”.

7.1.2 *Definition of Baseline*

Changes from baseline, percentage changes from baseline, and occurrence of disease reactivations will be calculated separately within each study phase (SAOL and RW), relative to the start of dosing during that phase:

- **SAOL Baseline:** Baseline during the SAOL phase will be defined as the last measurement reported prior to the first dose of open-label TA at Week 0 (V1)
- **RW Baseline:** Baseline during the RW phase will be defined as the last measurement reported prior to the first dose of double-blind study drug (TA or placebo) at Week 18 (V8)

7.1.3 *Summarization by Visit*

Data summarized by study visit will be based on the nominal, scheduled visit label as reported on the eCRF, except for data that are captured at early termination or unscheduled visits. Data collected at early termination or unscheduled visits will only be included in by-visit summaries if they fall within a scheduled post-baseline visit window (see Table 2) and there is no data from a nominal visit for that specific visit. If both an unscheduled visit and an early termination visit fall within the same visit window the early termination visit will be used for that specific visit.

Table 2 Visit Windows for Early Termination and Unscheduled Visits

Phase	Analysis Visit	Target Day	Visit Window
SAOL	Week 1	SAOL Day 7	$2 \leq \text{SAOL Day} \leq 11$
	Week 2	SAOL Day 14	$12 \leq \text{SAOL Day} \leq 18$
	Week 3	SAOL Day 21	$19 \leq \text{SAOL Day} \leq 25$
	Week 4	SAOL Day 28	$26 \leq \text{SAOL Day} \leq 42$
	Week 8	SAOL Day 56	$43 \leq \text{SAOL Day} \leq 70$
	Week 12	SAOL Day 84	$71 \leq \text{SAOL Day} \leq 105$
	Week 18	SAOL Day 126	$106 \leq \text{SAOL Day} \leq \text{End of SAOL Phase}$
	Week 20	RW Day 14	$2 \leq \text{RW Day} \leq 21$
	Week 22	RW Day 28	$22 \leq \text{RW Day} \leq 42$
	Week 26	RW Day 56	$43 \leq \text{RW Day} \leq 70$
	Week 30	RW Day 84	$71 \leq \text{RW Day} \leq 98$
	Week 34	RW Day 112	$99 \leq \text{RW Day} \leq \text{End of RW Phase}$

Note: SAOL Day is calculated as visit date – first SAOL dose date +1. RW Day is calculated as visit date – first RW dose date +1.

Data collected at all visits will be considered when endpoint derivations potentially include multiple visits (eg, determination of baseline value, determination worst post-baseline value, etc.). All data will be included in patient listings.

7.1.4 Data Handling Rules

Unless otherwise noted, values reported as greater than or less than some quantifiable limit (eg, “< 1.0”) will be summarized with the sign suppressed in summary tables and figures, using the numeric value reported. Data will display on patient listings to include the sign.

In some cases, CRP values from the central laboratory were entered as ‘< 3 mg/L’. Since the ULN for CRP is 1 mg/L, a value of < 3 mg/L does not allow determination of whether the CRP value is $\geq 2 \times \text{ULN}$. In these cases, a re-test of high sensitivity CRP will be attempted, and those values will be used to replace the < 3 mg/L value. If the high sensitivity CRP value is not obtained a local lab CRP value may be used to determine whether the CRP value is $\geq 2 \times \text{ULN}$.

7.1.5 Standard Calculations

Where appropriate, the calculated study day of each assessment or event will be presented with the assessment or event date on patient data listings. The calculated study day will be relative to the start of dosing within each phase:

- The assessment/event date minus the date of first dose received during the SAOL or RW phase, if the assessment/event date is prior to the date of first dose; and

- The assessment/event date minus the date of first dose received during the SAOL or RW phase, plus one, if the assessment/event date is on or after the date of first dose.

Other variables requiring calculations will be derived using the following formulas:

- **Days:** A duration between two dates expressed in days will be calculated using the following conventions:
 - Later date – earlier date + 1, if the earlier date is on or after the date of first dose of study drug during the SAOL or RW phase; or
 - Later date – earlier date, if the earlier date is prior to the date of first dose of study drug during the SAOL or RW phase.
- **Weeks:** A duration expressed in weeks will be calculated by dividing the duration in days by seven
- **Months:** A duration expressed in months will be calculated by dividing the duration in days by (365.25 / 12)
- **Years:** A duration expressed in years will be calculated by dividing the duration in days by 365.25
- **Change from Baseline:** Change from baseline will be calculated as the post-baseline value minus the baseline value
- **Percentage Change from Baseline:** Percentage change from baseline will be calculated as the change from baseline divided by the baseline value, multiplied by 100

7.1.6 *Patient Consideration for Original Study Design*

Patients enrolled under the original protocol through Protocol Amendment 2 (Version 3.0) and who were randomized to TA during the RDBPC phase of the study will be considered for all analyses, combined with those patients enrolled under Protocol Amendment 4 (Version 4.0), or any subsequent amendments. Patients randomized to placebo under the original study design will only be included in patient data listings and will be characterized separately in the CSR.

7.2 *Analysis Populations*

The analysis populations are defined as follows:

- **Single Arm Open-Label Full Analysis Set (SAOL-FAS):** All patients who are eligible and receive at least one dose of open-label TA at Week 0 (V1) under Amendment 3 (Version 4.0) of the protocol (or subsequent amendments), or at

least one dose of TA at Week 0 (V1) during the RDBPC phase under previous protocol amendments.

- Single Arm Open-Label PK Analysis Set (SAOL-PKAS): All patients in the SAOL-FAS who have sufficient plasma concentration data to calculate PK parameters. If any patients are found to be noncompliant with respect to dosing or have incomplete data, a decision will be made prior to DBL on a case-by-case basis as to their inclusion in the analysis.
- Randomized Withdrawal Full Analysis Set (RW-FAS): All patients who meet the criteria for randomization and are randomized to blinded study treatment during the RW phase.
- Randomized Withdrawal Per-Protocol Analysis Set (RW-PPAS): All patients in the RW-FAS who complete the RW phase up through Week 26 (V11) for protocol version 4.0/4.1 or Week 34 (V13) for protocol versions 5.0 and 6.0 or have disease reactivation and for whom no relevant protocol deviations (ie, major protocol deviations) were documented.

The analyses of safety and efficacy during the SAOL phase will be based on the SAOL-FAS and the analyses of safety and efficacy during the RW phase will be based on the RW-FAS. Additional exploratory analyses of efficacy during the RW phase will be performed based on the RW-PPAS. Analysis of PK plasma concentration data and PK parameters will be performed based on the SAOL-PKAS.

7.3 Study Patients

7.3.1 Disposition of Patients

Patient disposition will be presented separately for the SAOL phase and RW phase.

Summaries during the SAOL phase will include the number and percentage of patients in each analysis population, completing TA treatment during the SAOL phase, discontinuing TA early during the SAOL phase by reason for discontinuation, starting new medications for treatment of the patient disease, completing the SAOL phase, and discontinuing the SAOL phase early by the primary reason for discontinuation.

Summaries during the RW phase will be based on the RW-FAS and will be summarized by randomized treatment received during the RW phase. The summary will include the number and percentage of patients completing study treatment during the RW phase, discontinuing study treatment during the RW phase by reason for discontinuation, starting new medications for treatment of the patient disease, completing the RW phase, and discontinuing the RW phase early by primary reason for discontinuation.

7.3.2 Protocol Deviations

Major protocol deviations occurring during the RW phase will be summarized by treatment group and over all patients combined for the RW-FAS. Major protocol

deviations may include, but will not be limited to violation of eligibility criteria, randomization errors, lack of compliance with study drug dosing, or on-study administration of a prohibited medication.

All major protocol deviations will be determined and appropriately categorized prior to database lock and prior to breaking the blind of the treatment group assignments. The decision as to whether a protocol deviation is a major protocol deviation or a major protocol violation leading to exclusion from the RW-PPAS Analysis Set will be made on a case-by-case basis in a blinded data review meeting. The number and percentage of patients with any major protocol deviations as well as the number and percentage of patients with major deviations within each category will be presented.

All protocol deviations collected on study during either the SAOL phase or RW phase will be listed by patient to include the date the deviation occurred, type of deviation, and a description.

7.3.3 Demographic and Other Baseline Characteristics

Demographic variables including age, sex, ethnicity, and race will be summarized for the SAOL-FAS, SAOL-PKAS, RW-FAS, and RW-PPAS. Age as reported within the electronic data capture system will be summarized using descriptive statistics. Sex, ethnicity, and race will be summarized with the number and percentage of patients in each parameter category.

Baseline characteristics include disease history, other manifestations of intestinal dysfunction, other clinical symptoms of disease, medical history, disease-specific prior medication use, height, weight, and body mass index (BMI).

Disease history, other manifestations of intestinal dysfunction, and other clinical symptoms of disease will be summarized for the SAOL-FAS, RW-FAS, and RW-PPAS by treatment group and over all patients combined.

Height, weight, BMI, Medical history, and prior medication use will be summarized for the SAOL-FAS.

Height, weight, and BMI at baseline will be summarized using descriptive statistics. Frequency counts and percentages to summarize patients reporting abnormal medical history by body system will be presented.

Baseline disease history will be described by the time elapsed (months) since diagnosis of disease and the incidence of previous and current disease history by symptom. Time since diagnosis of disease will be calculated as described in [Section 7.1.4](#) where complete diagnosis dates are provided. If only the month and year are provided, the months since diagnosis will be determined as difference in months between the diagnosis month and year and the month and year of informed consent. If only the year of diagnosis is provided, the months since diagnosis will be determined as the difference between the diagnosis year and the year of informed consent, multiplied by 12. Months since diagnosis will be summarized using descriptive statistics. The number and percentage of

patients reporting each disease history symptom, including other manifestations of intestinal dysfunction and other clinical symptoms and/or signs, will be presented separately for previous history and current history.

Disease-specific prior medications will include those treatments specific to the treatment of the auto-inflammatory condition that started and stopped prior to the date the informed consent is signed, as reported on the Prior Medications eCRF. Medications will be coded using the World Health Organization Drug Dictionary Enhanced (WHODDE, version March 1, 2017). Medications entered on the eCRF will be mapped to Anatomic Therapeutic Chemical (ATC) drug class (level 4) and drug name. The number and percentage of patients receiving any prior medication will be summarized by treatment group and over all patients combined, as will the number and percentage receiving any medication by ATC drug class and generic drug name. Patients reporting use of more than one medication at each level of summarization (any prior medication received, ATC class, and generic drug name) will be counted only once. ATC class terms will be displayed by descending order of incidence, as will generic drug names within each ATC class.

7.3.4 Measurements of Treatment Compliance

Compliance to the study treatment regimen will be determined as the total number of days with a dose received divided by the expected number of days with a dose received, multiplied by 100. The total number of days with a dose received will be determined by phase based on entries on the Study Drug Administration form, where a dose received is counted for a given day if the response to “Was the study drug administered” is “Yes.” The expected number of days with a dose received will be calculated as the date of last dose of study drug minus the date of first dose of study drug plus one, divided by two. Calculations that result in a value with a remainder of one half (ie, the number of days between doses is an odd number) will be rounded up to the next largest integer. The date of last dose of study drug is the date reported on the End of Treatment form, for both the end of double-blind treatment and the end of treatment during the RW phase.

Dosing compliance will be summarized using descriptive statistics, by treatment group, based on the SAOL-FAS for dosing during the SAOL phase and based on the RW-FAS for dosing during the RW phase. The number and percentages of patients who are < 80% compliant and ≥ 80% compliant within each treatment group will be summarized.

7.4 Efficacy Evaluation

7.4.1 Datasets Analyzed

All efficacy summaries for data collected during the RW phase will be based on the RW-FAS; selected efficacy summaries will also be produced on the RW-PPAS provided the RW-FAS and RW-PPAS differ by at least one patient. A data listing of patients excluded from the RW-FAS or RW-PPAS, including the reason for exclusion, will be presented.

All efficacy summaries of data collected during the SAOL phase will be based on the SAOL-FAS.

7.4.2 Primary Efficacy Endpoint Analysis Methods

The primary efficacy endpoint is the time to first occurrence of disease reactivation (including full and partial disease reactivation) during the 16-week RW phase, as defined in [Section 6.4.1.1](#).

7.4.2.1 Primary Estimand of the Primary Efficacy Endpoint

The primary estimand for the primary endpoint will be described as follows:

Population: All patients in the RW-FAS population.

Endpoint: Time to first occurrence of disease reactivation during the RW phase.

Intercurrent events:

- End of RW phase: patients who do not experience a disease reactivation and complete the RW phase will be censored at the time of their last disease assessment during the RW phase regardless of the length of the RW phase (according to the protocol version the patient was treated under).
- Rescue immunosuppression treatment: patients who receive rescue immunosuppression treatment without objective disease reactivation and continue in the RW phase will be censored at the time of their last disease assessment during the RW phase, including assessments up to the start day of the rescue immunosuppression treatment.
- Clinical signs of inflammation that are not disease related: patients who present with clinical or laboratory signs of inflammation meeting the criteria of disease reactivation that are determined by the treating physician to be related to an infection rather than disease reactivation and are resolved after repeat assessments within the visit window will not be considered to have a disease reactivation at that visit (see [Section 7.4.2.2](#)).

Population-level summary: Kaplan-Meier (KM) estimates of the survival curves by treatment group, hazard ratio including 95% CI, and log-rank test.

The primary efficacy analysis will test the following hypothesis:

- H_0 : The survival distribution of time to first occurrence of disease reactivation during the RW phase is equal between TA and placebo
- H_1 : The survival distribution of time to first occurrence of disease reactivation during the RW phase is different between TA and placebo

TA will be compared to placebo using the log rank test. Kaplan-Meier (KM) estimates of the distribution of time-to-event will be summarized and graphed by treatment group. Greenwood's formula will be used to estimate the standard error of the KM statistic. The

primary analysis endpoint will be tested at a 2-sided alpha level of 0.05. The summarization will include the KM estimate of the median, 25th and 75th quartiles, and corresponding 95% CI, if estimable. Summaries will include the “at-risk patient” counts at the scheduled post-baseline visits during the RW phase. The number and percent of patients experiencing a disease reactivation and censored will be presented. The hazard ratio and 95% CI will be determined based on a Cox regression model with a single factor for treatment group.

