4 INTRODUCTION

The purpose of this statistical analysis plan (SAP) is to provide comprehensive and detailed descriptions of the methods and presentation of data analyses proposed for AB2 Bio Ltd Protocol NLRC4/XIAP.2016.001 (Multicenter, placebo-controlled, randomized withdrawal trial with Tadekinig alfa [r-hIL-18BP] in patients with interleukin-18 [IL-18] driven monogenic auto-inflammatory conditions: NLRC4 mutation and XIAP deficiency). Descriptions of planned analyses are provided in order to avoid post hoc decisions that may affect the interpretation of the statistical analysis. The statistical methods applied in the design and planned analyses of this study are consistent with the International Council for Harmonisation (ICH) guideline *Statistical Principles for Clinical Trials* (E9) (1998).

This SAP will be finalized prior to data analysis, before breaking the treatment blind on the Randomized Withdrawal (RW) phase, and prior to database lock to provide full details, including templates for tables, listings, and figures, to be presented in the clinical study report (CSR). Any changes between the statistical methods provided in the clinical study protocol and this SAP will be explained herein; any changes or deviations from this SAP relative to the final analysis will be fully documented in the CSR. Minor changes or deviations from the templates for tables, figures, and listings need not be documented in the CSR.

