7.4.2.3 Sensitivity Analyses of the Primary Efficacy Endpoint

The primary endpoint analysis will be repeated on the RW-PPAS, provided the RW-FAS and RW-PPAS differ by at least one patient.

In addition, the following tipping point analyses will be performed for the primary endpoint to assess the impact of the different lengths of the RW phase due to the different versions of the protocol. For patients enrolled in protocol versions 4.0/4.1 and earlier whose planned RW duration was only 8 weeks and had no disease reactivation during the RW phase:

1. A worst-case imputation will be applied to patients in both treatment groups by assigning patients as having disease reactivation at the next day after the last per protocol visit.
2. A best-case imputation will be applied to patients in both treatment groups by assigning patients as not having disease reactivation until Week 16 of the RW phase.
3. A worst-case imputation will be applied to patients in the TA treatment group and a best-case imputation will be applied to patients in the Placebo treatment group.

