7.4.4.1 Best Response to Therapy During SAOL

The number and percent of subjects in each response category will be summarized, including: complete response, partial response, disease improvement, and no improvement or not evaluated.

7.4.4.2 *Treatment Failures during RW*

Patients meeting the criteria for treatment failure during the RW phase will be summarized by the number and percent of patients in each treatment group. The estimated difference in percentages (TA – placebo) among treatment failures between treatment groups will be presented along with the associated 95% exact CI. The 95% CIs for difference in binomial proportions will be computed based on exact unconditional confidence limits using the score statistic. Treatment groups will be compared for response to therapy versus treatment failure using the Fisher's exact test.

The estimand for this secondary endpoint will be described as follows:

Population: All patients in the RW-FAS population.

Endpoint: Treatment failure (Yes/No).

Intercurrent events: All patients who experience disease reactivation during the RW phase will be counted as treatment failure regardless of intercurrent events.

Population-level summary: Number and percentage of treatment failures, exact unconditional 95% CIs using the score statistic, and Fisher's exact test.

7.4.4.3 *Change from Baseline in C-reactive Protein and Serum Ferritin*

Descriptive statistics for the observed CRP and serum ferritin values and the changes from RW Baseline during the RW phase will be presented by visit for each treatment group. Descriptive statistics will include number of subjects, mean, standard deviation, 95% CI of the mean, median, Q1, Q3, minimum, and maximum values. Mean CRP and serum ferritin values with associated standard error bars will be plotted by treatment group over time during the RW phase. The primary comparison of change from RW Baseline values among treatment groups will be based on the Mann-Whitney-Wilcoxon test. As sensitivity analyses, the mean change from RW baseline will also be compared among treatment groups using Welch's two-sample test that allows for unequal variances, as well as by a linear regression model with Huber-white sandwich errors allowing for heteroscedasticity.

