7.6 Determination of Sample Size

The primary endpoint of the study is time to first occurrence of disease reactivation (including full and partial disease reactivation) during the RW phase of the study. There is limited historical data for this disease condition, for either a control or an experimental test product, however the frequent recurrence of disease reactivations was expected in the control arm ([Wada 2014](#)). Originally, an 8-week event rate is assumed to be 90% in the placebo group and a considerable reduction in disease reactivations for patients receiving TA was expected. However, a lower event rate was observed from the currently enrolled (still blinded) patients. Thus, the RW phase is prolonged to a maximum of 16 weeks to better assess the effect of TA withdrawal. The power calculations below will assume the same 90% event rate in the SOC arm at 16 weeks. [Figure 1](#) below displays the power achieved for a two-arm study and assumes the following:

- Two-sided log-rank test, with input based on the proportion of patients surviving (ie, event-free) at 16 weeks
- Two-sided alpha = 0.05
- A 1:1 randomization of 10 patients (ie, 5 patients per arm)
- The proportion of patients surviving (ie, event-free) in the control arm at Week 16 of the RW phase is 0.1, which equates to a 90% event rate
- No patients in either group drop out of the study prior to experiencing a disease reactivation or completing the 16 week treatment period as planned
- Total study time is 32 weeks, including a 16-week accrual period and a 16 week follow-up time
- Varying levels of a hazard ratio, from 0.1 to 0.25 in 0.05 increments

Figure 1 Power vs. Hazard Ratio

A hazard ratio of 0.1 equates to an assumed 16-week event rate in the TA group of 20.6% (ie, a survival event-free rate of 79.4%). These assumptions achieve 78.4% power based on a two-sided log rank test with an overall sample size of 10 patients to be randomized in the RW phase (5 in the placebo group and 5 in the TA group). A hazard ratio of 0.1 results in an assumed number of total events among 10 patients to be 6.7, with 4.9 occurring in the placebo group and 1.8 occurring in the TA group.

No power calculations were performed for the SAOL phase of the study, as analysis will be descriptive in nature.

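### The Cox hazard ratio in the primary estimand's summary has no finite value in about two of five trials at the design effect, and the SAP states no rule for that case

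*SAP*

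**What the plan says.** SAP 7.4.2.1 tests the primary endpoint, time to first disease reactivation in the randomized withdrawal (RW) phase, with a two-sided log-rank test at 0.05. The estimand's population-level summary consists of Kaplan-Meier curves plus "hazard ratio including 95% CI, and log-rank test". The section then adds: "The hazard ratio and 95% CI will be determined based on a Cox regression model with a single factor for treatment group". It names no interval type, no tie method and no action if the model has no finite solution.

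The nearest wording, "and corresponding 95% CI, if estimable", belongs to the sentence on the Kaplan-Meier quartiles. SAP 7.1.1 covers only how intervals are rounded and displayed, and SAP 7.7 does not take the point up. Protocol 16.6.1 names the log-rank test and Kaplan-Meier estimates but no Cox model.

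Elsewhere the SAP does choose small-sample methods. For treatment failures (7.4.4.2) it says: "The 95% CIs for difference in binomial proportions will be computed based on exact unconditional confidence limits using the score statistic". SAP 7.4.3 uses Clopper-Pearson limits.

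**The concern.** A Cox model with one binary factor has a monotone partial likelihood when every event that occurs while both arms still have patients at risk belongs to the same arm. The estimated hazard ratio then runs to zero (or infinity) and a Wald interval is unusable. With 5 patients per arm and a large expected effect, this is a likely outcome.

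The hazard ratio is the only between-group effect size on the time-to-event scale in the primary estimand's summary. It would be missing mainly when the result is most clearly positive. SAP section 4 says the planned analyses are described "in order to avoid post hoc decisions that may affect the interpretation of the statistical analysis", and the SAP text leaves this case open.

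**Working it through.** **Inputs.** From SAP 7.6: 5 patients per arm, two-sided 0.05, placebo event-free proportion 0.1 at Week 16, no dropout, and "Varying levels of a hazard ratio, from 0.1 to 0.25 in 0.05 increments". From SAP 6.1.3: at most 16 weeks of RW treatment, with visits at RW weeks 2, 4, 8, 12 and 16. Exponential times are my assumption, so the placebo hazard is λ = ln(10)/16 = 0.1439 per week.

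**The plan's own figures.** The Tadekinig alfa event rate at a hazard ratio of 0.1 is 1 − 0.1^0.1 = 20.57% (stated 20.6%). Expected events over 16 weeks are 5 × 0.9 + 5 × 0.2057 = 5.53. Schoenfeld's formula then gives 77.2% power, within 2 points of the stated 78.4%. The stated 6.7 events correspond to longer follow-up, about 32 weeks for every patient. I use the 16-week cap. With 16 weeks of accrual and follow-up to week 32, the shares below would be 38.9% (hazard ratio 0.1) and 12.3% (0.25).

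**Probability of no finite hazard ratio (HR).** Two patterns matter; the mirror case, with all such events on Tadekinig alfa, is negligible.
- No Tadekinig alfa event: 0.1^(5·HR). At 0.1 this is 0.1^0.5 = 31.6%; at 0.25 it is 0.1^1.25 = 5.6%.
- Tadekinig alfa events only after the last placebo patient has reactivated: ∫₀¹⁶ 5λe^(−λu)(1−e^(−λu))⁴ [e^(−5λ·HR·u) − e^(−5λ·HR·16)] du. This is 10.0% at 0.1 and 7.5% at 0.25.

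| Hazard ratio | No Tadekinig alfa event | Total, exact times | Total, events dated at scheduled visits |
|---|---|---|---|
| 0.10 | 31.6% | 41.6% | 38.0% |
| 0.15 | 17.8% | 27.7% | 24.0% |
| 0.20 | 10.0% | 18.9% | 15.4% |
| 0.25 | 5.6% | 13.1% | 10.1% |

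Simulation and direct maximisation of the partial likelihood agree, scattering over about 38–42% at 0.1 and 10–14% at 0.25.

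**Departures from the planning case.** SAP 7.6 reports: "However, a lower event rate was observed from the currently enrolled (still blinded) patients". At an assumed 70% placebo rate the shares are about 56% (0.1) and 23–24% (0.25), with simulation runs reaching 58% and 26%. SAP 7.4.2.3 also refers to patients "whose planned RW duration was only 8 weeks and had no disease reactivation during the RW phase" and gives no count. If 2 or 4 of the 10 had the shorter phase, split evenly by arm, the shares at the 90% rate are 43–50% (0.1) and 13–19% (0.25).

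**Where it falls.** At the 90% rate and a hazard ratio of 0.1, 98–99% of monotone trials have log-rank p < 0.05; at 70% it is about 76–84%. Conversely, at 90% and 0.1, 53–59% of log-rank-significant trials have no finite hazard ratio.

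**Worked case: 5/5 placebo events at different times, 0/5 on Tadekinig alfa.**
- Log-rank: expected Tadekinig alfa events 5/10 + 5/9 + 5/8 + 5/7 + 5/6 = 3.228, variance 1.074, chi-square 3.228²/1.074 = 9.70, p = 0.0018.
- Ordinary hazard ratio: no finite estimate. The one-sided profile bound solves Σ log(1 + 5θ/j) = 1.92 over j = 1 to 5, giving θ = 0.218.
- Firth-penalised Cox: 0.039, profile limits 0.0003 to 0.38.
- Treatment-failure difference: −100 points, exact upper limit 1 − 2 × 0.025^(1/10) = −0.383.

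**Interval type when the estimate is finite.** At 90% and 0.1, a finite Wald interval includes 1 despite a significant log-rank test in about 13% of all trials. With ordinary profile limits the disagreement is 0.5–0.7%.

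**The case against.** **Nothing confirmatory depends on the hazard ratio.** This stands. The hypothesis is tested by the log-rank test, and the hazard ratio has no place in the SAP 7.4.5.5 hierarchy. A reader might infer that the primary analysis fails in two of five trials; the documents do not support that. The test, the curves and the exact treatment-failure interval remain defined, and a 5/5 versus 0/5 result would be well described by them. What is lost is the time-to-event effect size.

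**The rule may exist elsewhere.** A reader might infer that the choice will be made after unblinding. That cannot be shown: SAP section 4 refers to output templates that are not among the documents. What can be said is that the SAP text states no rule.

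**Ties.** A reader might infer that the missing tie method is a serious gap. If every event fell exactly on a visit day, about 96% of trials at a hazard ratio of 0.1 would have a tied event time. But SAP 6.4.1.1 uses actual dates and counts unscheduled visits, and the protocol's schedule of events allows ±3 days. With visit days uniform over that window (an assumption), ties fall to about one third of trials, and the disagreement of profile limits with the log-rank test is 0.75% with Breslow against 0.40% with Efron. The effect is small.

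**Wald limits.** Counting every significant trial without a Wald interval that excludes 1 gives 51–54%, but most of those are the monotone trials already counted. Only the 13% or so with finite intervals are additional. The SAP also does not say that Wald limits will be used.

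**A simpler remedy would do.** Stating the interval type and a not-estimable entry would close the gap in the rule, but leave the estimand without its time-to-event effect size in the planned success case. Inverting the score test is another reasonable route; it was not evaluated here.

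**Conclusion.** The point holds as a gap that should be fixed, not as a threat to the trial's conclusion. As written, the Cox model gives no usable hazard ratio in about 38–42% of trials at 0.1, the effect behind the stated 78.4% power, and in 10–13% at 0.25. The share grows with a lower placebo rate or with patients on the 8-week RW phase. These figures rest on 5 patients per arm, exponential times with proportional hazards and no dropout. The 70% placebo rate and the number of 8-week patients are my assumptions. That the problem falls almost wholly in log-rank-significant trials is specific to the 90% rate and weakens at 70%.

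**What to change.** In SAP 7.4.2.1, before unblinding:

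1. Keep the single-factor Cox model, with profile-likelihood 95% limits rather than Wald limits. Name Efron ties, for completeness only.
2. Define the monotone case as every event with both arms at risk falling in one arm. Then report the ordinary hazard ratio as not estimable and give the Firth-penalised Cox estimate with profile-likelihood 95% limits as the effect size, labelled as shrunk towards 1. Show any one-sided ordinary profile bound only beside it.
3. Apply the same rule to the repeats of the analysis in SAP 7.4.2.3.

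The log-rank test, alpha and sample size do not change; the cost is a few lines of text and code.

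The remedy has drawbacks. Firth limits cover 96–97% at the 90% rate, but the median estimate is 0.135 for a true 0.10. They include 1 despite a significant log-rank test in about 3–5% of trials at 90% and a hazard ratio of 0.1, and in 15–17% at 70%. Ordinary profile limits cover about 98% at 0.1–0.2 but 87–90% at 0.25. Within monotone trials at 0.25 they cover only 19–23%, against 100% for Firth, because a bound of 0.218 misses a true 0.25. That is why the bound should not stand alone.
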